4.2.4.16. Psoriatic Arthritis Disease Activity Score (PASDAS)

The PASDAS is a weighted index comprised of assessments of joints, function, acute phase response, QoL, and patient and physician visual analogue scores (VAS) (Coates, 2014).

Note: This study does not utilize VASs, but rather NRSs. The patient's and physician's global assessment of disease activity captured on a NRS will be multiplied by a factor of 10 to derive the VAS, used to calculate PASDAS.

The calculation of the PASDAS will be performed programmatically using the formula below:

$$\text{PASDAS} = [(0.18 \times \sqrt{\text{physician global VAS}}) + (0.159 \times \sqrt{\text{patient global VAS}}) - (0.253 \times \sqrt{\text{SF36-PCS}}) + (0.101 \times \text{LN (SJC66 +1)}) + (0.048 \times \text{LN (TJC68 +1)}) + (0.23 \times \text{LN (Leeds enthesitis count+1)}) + (0.377 \times \text{LN (dactylitis count+1)}) + (0.102 \times \text{LN (CRP+1)+2})] * 1.5.$$

CRP = C-reactive protein; LN = natural logarithm; PCS = physical component summary scale of SF36; SF36 = Medical Outcomes Study Short Form-36; SJC = swollen joint count; TJC = tender joint count; VAS = visual analogue scale. All VAS scores are 0–100 mm. Swollen joint count is 66 joints, and tender joint count 68.

Note: SJC66 and TJC68 will be used in the derivation of PASDAS, refer section 4.2.4.13. If one or more components are missing, then PASDAS is set to be missing. The score range of the PASDAS is 0–10, with worse disease activity represented by higher scores. Response criteria for the Psoriatic Arthritis Disease Activity Score (PASDAS) is detailed in Table 4. PASDAS Score Over 48 Weeks will be presented graphically.

Table 4: Response criteria for PASDAS

Final PASDAS Score	Improvement		
	≥ 1.6	< 1.6 BUT > 0.8	≤ 0.8
≤ 3.2	1	2	3
> 3.2 but < 5.4	2	2	3
≥ 5.4	2	3	3

1: good response; 2: moderate response; 3: poor response

4.2.4.17. Health Assessment Questionnaire-Disability Index (HAQ-DI) Score

The HAQ-DI is composed of 20 items in 8 categories (Dressing and Grooming, Arising, Eating, Walking, Hygiene, Reach, Grip, Activities). Each category has 2 or 3 items. For each item, there are 4 response options: without any difficulty, with some difficulty, with much difficulty, and unable to do (scored 0-3, respectively). The HAQ-DI score will be set to missing if a subject does not have values for at least 6 of the 8 categories.

Computing the HAQ-DI Score will follow the 2 steps below:

1. Find the highest score for each category. If use of aids/devices and/or help from another person are indicated, adjust the highest score for the associated category by increasing a lower score, which is between 0 and 2, to represent underlying disability more accurately. For example, if use of aids/devices and/or help from another person are indicated, adjust the highest score to 2 if the highest score is a 0 or a 1. If the highest score is 2 or 3, retain the value.
2. Sum the highest scores from all categories answered and divide it by the number of categories answered (must be a minimum of 6) to obtain an HAQ-DI score of 0-3 (3=worst functioning).

Please note, only one score will be calculated per HAQ-DI assessment.

If the “other” category is checked on the HAQ-DI assessment, then this is expected to be an aide not associated for any of the existing categories, thus this will be excluded from the HAQ-DI score calculation.

Data resource: HAQ-DI is entered by the patient via site pad provided by ERT.

Change from baseline in HAQ-DI score over 48 weeks will be presented graphically.

4.2.4.18. Bath Ankylosing Spondylitis Disease Activity Index (BASDAI) Score

The BASDAI consists of 6 questions to assess 5 major symptoms (fatigue, spinal pain, peripheral joint pain/swelling, areas of localized tenderness, and morning stiffness), with each answered on a 0- to 10-unit NRS. To give each of the 5 symptoms equal weighting, the mean of the two

scores relating to morning stiffness (questions 5 and 6) is taken. Each of the other 4 questions counts as 1 item by itself. The final BASDAI score is defined by calculating the mean of the 5 items. The BASDAI score ranges from 0 to 10, with higher scores reflecting greater disease activity. In case any of the scores for questions 1-4 is missing, or the scores for both questions 5 and 6 are missing, the BASDAI score will be set to missing. In case of a missing score for either question 5 or 6, the score for the other question answered will be used as the mean of questions 5 and 6.

Data resource: BASDAI is entered by patient via site pad provided by ERT.

BASDAI score over 48 weeks will be presented graphically.

4.2.4.19. Psoriatic Arthritis Impact of Disease 12-domain Questionnaire (PsAID-12)

The PsAID consists of 12 physical and psychological domains and is based on 0- to 10-unit NRS. Each domain is rated as a number between 0 and 10. The final PsAID score is the sum of each domain with different weighting and divided by 20 as below.

[figure not shown]
Final PsAID value = [(PsAID1 (pain) NRS value (range 0-10) x 3)
+ (PsAID2 (fatigue) NRS value (range 0-10) x 2)
+ (PsAID3 (skin) NRS value (range 0-10) x 2)
+ (PsAID4 (work and/or leisure activities) NRS value (range 0-10) x 2)
+ (PsAID5 (function) NRS value (range 0-10) x 2)
+ (PsAID6 (discomfort) NRS value (range 0-10) x 2)
+ (PsAID7 (sleep) NRS value (range 0-10) x 2)
+ (PsAID8 (coping) NRS value (range 0-10) x 1)
+ (PsAID9 (anxiety) NRS value (range 0-10) x 1)
+ (PsAID10 (embarrassment and/or shame) NRS value (range 0-10) x 1)
+ (PsAID11 (social life) NRS value (range 0-10) x 1)
+ (PsAID12 (depression) NRS value (range 0-10) x 1)]/20

[figure not shown]
The final score has a range from 0 (best status) to 10 (worst status) with a cut-off of 4 ([Gossec, 2014](#)).

[figure not shown]
If one of the 12 domains composing the PsAID is missing, it will be imputed by the mean value of the 11 non-missing NRS scores. If two or more of the domains are missing, the final PsAID score will be considered as missing.

Data resource: PsAID-12 is entered by patient via site pad provided by ERT.

PsAID-12 score over 48 weeks will be presented graphically.

4.2.5. Derivations of Safety Endpoints

Baseline definition for all safety endpoints is given in Section 5.4. Change from baseline is calculated as on-treatment value minus the baseline value. Handling of time points is described in Section 5.5.

4.2.5.1. Treatment-Emergent Adverse Event

A treatment-emergent adverse event (TEAE) is defined as any AE that begins or worsens on or after the date of the first dose of investigational product (IP) and no later than 28 days after the

last dose of IP for subjects who have completed the study or have discontinued early by the time of database cut.

If the treatment-emergent status of an AE is unclear due to a missing/incomplete start date, it will always be considered treatment-emergent, unless shown otherwise by data. Date imputation rules for partially missing AE start dates are described in Appendix [A1 1.1](#).

4.2.5.2. Treatment-emergent Adverse Events Leading to Drug Withdrawal, Leading to Drug Interruption, and Leading to Death, and Drug-related Treatment-emergent Adverse Events

A TEAE leading to drug withdrawal is a TEAE for which the investigator indicates that the action taken with respect to IP is withdrawn permanently (action taken on AE eCRF is recorded as “DRUG WITHDRAWN”). A TEAE leading to drug interruption is a TEAE for which the investigator indicates that the action taken with respect to IP is drug interrupted. A TEAE leading to death is a TEAE for which the outcome is fatal. Relationship to IP is based on the investigator's causality judgment; that is, a drug-related AE is an AE indicated by the investigator to have a suspected relationship to IP.

4.3. Sample Size and Power

While no MRI data are available for apremilast, assumptions used for the sample size calculation are primarily derived from the literature ([Glinatsi, 2015](#)). With an approximate 20% dropout rate, a sample size of 120 is required to produce a two-sided 95% confidence interval, for the expected change from baseline in the composite score of BME, synovitis, and tenosynovitis, with a distance from the mean to the limit equal to 1.24, assuming the standard deviation is 6.2.

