4.2.4.3.1. Synovitis

Synovitis is to be scored 0-3 at MCP, PIP and DIP joints of fingers 2 to 5. Grading scale: score 0 is normal, while score 1-3 is mild, moderate, severe, respectively. A total of 12 joints in the most affected hand are evaluated, the maximum possible score is 36.

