4.2.4.3.2. Flexor Tenosynovitis

Flexor tenosynovitis is to be scored 0-3 at the same 12 joint regions as evaluated for synovitis. The maximal thickness of enhancing/bright signal tenosynovium is to be assessed as follows: 0: none; 1: < 1/2 tendon thickness; 2: ≥ 1/2 and < 1 tendon thickness; 3: ≥ 1 tendon thickness. Like the synovitis score in Section 4.2.4.3.1, the maximum possible score is 36.

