4.2.4.3.4. BME score assessed by PsAMRIS

Bone marrow edema score, the bone edema score from PsAMRIS, is assessed on a scale of 0-3, based on the proportion of bone with edema, compare to the “assessed bone volume”, judged on all available images; where 0: no edema; 1: 1–33% of bone oedema; 2: 34–66% of bone oedema; 3: 67–100% of bone oedema (as per RAMRIS¹). A total of 12 joint regions are evaluated, and as each joint has proximal and distal components, thus the maximum possible score is 72.

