4.2.4.3.7. Inflammation Score of BME, Synovitis and Tenosynovitis

To give each of the three symptoms equal weighting, the inflammation score of BME, synovitis and tenosynovitis is the [REDACTED]. The maximum possible score is 216.

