4.2.4.3.8. Composite Score of BME and Synovitis

The composite score of BME and synovitis is the [REDACTED] like the inflammation score estimation in Section 4.2.4.3.7. The maximum possible score is 144.

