4.2.4.3.9. Total Inflammation Score

The total inflammation score consists of BME, synovitis, tenosynovitis and periarticular inflammation. The total inflammation score is computed as [REDACTED]

[REDACTED]. The maximum possible score is 288.

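### Do the SD of 6.2 and half-width of 1.24 in SAP 4.3 belong to a different scale from the SAP's 0–216 primary score?

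*SAP*

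**What the plan says.** SAP 4.3 carries over the sample-size statement of Protocol 9.3. Allowing for about 20% dropout, 120 subjects give a two-sided 95% confidence interval for the mean change in the composite of BME, synovitis and tenosynovitis, "with a distance from the mean to the limit equal to 1.24, assuming the standard deviation is 6.2". Both sections say the assumptions come mainly from a published validation study of PsAMRIS. Neither gives a range or weights for the composite.

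The SAP defines the score in 4.2.4.3.7. The formula is blacked out, but its aim is visible ("To give each of the three symptoms equal weighting") and so is its range: "The maximum possible score is 216". The component ranges are:

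- synovitis (SAP 4.2.4.3.1): "A total of 12 joints in the most affected hand are evaluated, the maximum possible score is 36";
- flexor tenosynovitis (SAP 4.2.4.3.2): "the maximum possible score is 36";
- BME (SAP 4.2.4.3.4): "as each joint has proximal and distal components, thus the maximum possible score is 72".

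Protocol Table 12 names the primary score by joining the three components with plus signs. Its description column calls it a composite score and gives neither weights nor a range.

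**The concern.** The three component maxima add to 144, not 216, so the SAP's primary score cannot be the plain sum. If Table 12 is read as a plain sum, the SAP has changed the score and kept the SD and half-width of the old one.

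In a single-arm study sized on precision, the SD and half-width are the whole quantitative case for 120 subjects. If 6.2 is the SD of change in the plain sum, the interval on the SAP's score should be wider in points than the 1.24 stated. The weights could also matter to interpretation, because BME's share of the range falls from 72/144 = 50% to 72/216 = 33%.

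**Working it through.** **Reproducing the plan's figure.** Inputs from SAP 4.3: SD 6.2, half-width 1.24, two-sided 95%, dropout 20%.

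- Completers needed: (1.96 × 6.2 / 1.24)² = 9.8² = 96.04.
- Enrolled: 96.04 / 0.80 = 120.05, so 120.
- Check: 120 × 0.80 = 96 completers, and 1.96 × 6.2 / √96 = 1.240. With a t quantile it is 1.256.

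The figure of 120 follows from its inputs.

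**What the SAP's score is.** All four SAP composites fit one rule, the number of components times the largest component maximum.

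| Composite | Plain sum of maxima | SAP maximum | Rule |
|---|---|---|---|
| BME, synovitis, tenosynovitis | 144 | 216 | 3 × 72 |
| BME, synovitis | 108 | 144 | 2 × 72 |
| Total inflammation | 168 | 288 | 4 × 72 |
| Total damage | 252 | 480 | 2 × 240 |

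So the primary score behaves as B + 2S, where B is BME and S is synovitis plus tenosynovitis. These weights are inferred from the visible maxima.

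**What would follow if 6.2 belonged to the plain sum B + S.** This is an assumption; the documents do not say so. Take 96 completers and an interval based on the raw SD.

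- Proportional scaling: 6.2 × 216/144 = 9.3, and the half-width is 1.96 × 9.3 / √96 = 1.86. As a share of the range nothing changes: 1.24/144 = 1.86/216 = 0.86%.
- Limits: Var(B + 2S) − Var(B + S) = 3 Var(S) + 2 Cov(B, S). If the covariance is not negative, the SD lies between 6.2 (only BME varies) and 12.4 (BME does not vary), so the half-width lies between 1.24 and 2.48. With negative covariance these limits need not hold; the two SDs are also equal when Cov(B, S) = −1.5 Var(S).

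A tighter range needs component SDs and correlations, which the documents do not give.

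**If 6.2 is already on the 0–216 scale,** 1.24 is correct as it stands.

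**Do the plus signs settle it?** No. The SAP's endpoint list (4.2.1.2) and its baseline list (9.2) write the total damage score as erosion plus bone proliferation. SAP 4.2.4.3.10 then gives those two components equal weight and a maximum of 480 instead of 252. In these documents a plus sign can simply list the parts of an equal-weight score.

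**The case for a change.** The strongest case for a change is that the half-width is the only stated basis for N, that a reader cannot tell which score it describes, and that naming the scale would cost a sentence. Proportional scaling is also a convenient case. When components respond differently, the weights alter how clearly a change shows. With equal, independent component SDs, the ratio of mean change to SD on the SAP's score, relative to the plain sum, is 0.96 if all three components change equally, 1.15 if only synovitis and tenosynovitis change, and 0.58 if only BME changes. Keeping a half-width of 1.24 at SD 9.3 would take 217 completers, or 272 enrolled.

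The labelling gap is real, and so is the point that 216 is not a plain sum. The rest does not carry. Nothing in the documents supports the BME-only pattern. Protocol 1.3.1.2 reports high responsiveness especially for synovitis and tenosynovitis, which under the same assumptions favours the SAP's weighting. The figure of 272 asks for the same number of points on a wider scale, and no margin or clinically important difference is tied to 1.24. Choosing the plain sum as primary would be a preference between two defensible scores. A separate plain-sum table would add only that sum's own SD and interval. BME, synovitis and tenosynovitis are each secondary endpoints at Weeks 24 and 48, with 95% intervals under Protocol 9.6.2, so on a common set of subjects the plain-sum mean change is the sum of three reported means.

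**Conclusion.** No change follows. SAP 4.3 leaves the scale of 6.2 unnamed, but the documents do not show that 1.24 is wrong, and only the cited publication could settle it. If 6.2 is on the 0–216 scale, the statement is right. If it is on the plain sum, the expected half-width on the SAP's score is 1.86 under proportional scaling and 1.24 to 2.48 with non-negative covariance, both assuming 96 completers and a raw-SD interval. The reported interval may instead be model-adjusted, since SAP 6.2.2.1 refers to scanner type, baseline score and time.

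In either case the analysis is unaffected. The planning SD enters no reported result, and the study will give a descriptive interval on the 0–216 score from the observed SD, with each component shown separately. The SAP calls itself a more detailed elaboration of the protocol, so supplying weights that Table 12 leaves open is within its purpose. This is a missing label that an analyst can read past without harm.

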5. GENERAL STATISTICAL CONSIDERATIONS

5.1. Reporting and Analysis Conventions

Summary statistics for continuous variables include sample size (n), mean, standard deviation (SD), median, minimum, the 25th (Q1) and 75th (Q3) percentiles, and maximum. All mean and median values will be formatted to one more decimal place than the measured value. SD values will be formatted to two more decimal places than the measured value. Minimum and maximum values will be presented to the same number of decimal places as the measured value.

Frequency summary for categorical variables includes number and percentage. All percentages will be rounded to one decimal place, unless presenting two decimal places is necessary when the percentages are very small. Number and percentage values will be presented as xx (xx.x%).

All analysis and summary tables will have the population sample size for the treatment in the column heading. P-values (2 sided) will be presented with 4 decimal places. All laboratory data except for hs-CRP will be reported using standard international (SI) units; hs-CRP will be reported in mg/dL.

Change from baseline will be calculated as (post-baseline minus baseline value).

Percent (%) change from baseline will be calculated as (post-baseline minus baseline value) divided by (baseline value), then multiply by 100. If a baseline value is zero, the percent change from baseline value will be excluded from the summaries.

Subject data listings will be provided to support the tables and graphs will be provided for selected parameters.

5.2. Definition of Analysis Populations

5.2.1. Full Analysis Set

The Full Analysis Set (FAS) will be the primary population for efficacy analyses. The FAS will consist of all subjects who are enrolled in the study. Subjects who are enrolled but do not receive any dose of IP will be excluded from FAS.

5.2.2. Modified Intent to Treat (mITT)

The mITT will consist of all subjects who are in FAS, have baseline and at least one postbaseline of primary efficacy endpoint PsAMRIS. mITT might be the population for the sensitivity analysis for the primary efficacy endpoint if needed.

5.2.3. Per-protocol Population

The Per Protocol (PP) population will consist of all subjects who receive at least one dose of study medication and have no major protocol violations which might affect primary efficacy endpoint. The final determination of major protocol violation criteria will be made prior to the database lock and will be documented.

5.2.4. Safety Population

The Safety population will consist of all subjects who received at least one dose of study medication.

5.3. Analysis Periods

In this study, the analysis periods are divided into open label treatment period and observational follow-up period below.

- Open label treatment period – Week 0 to Week 48

This period starts on the day after the first IP is dispensed (Visit 2/Week 0), and stops on either: (1) the completion date of treatment period collected in the eCRF; or (2) the early termination date of treatment period collected in the eCRF; or (3) the last known study date if the subject is lost to follow-up.

- Observational follow-up period – 4 weeks

Subjects who complete the study or early terminate from the study, will be followed up for 28 days after the Visit 7/Week 48 or Early Termination visit. The period starts at the end date of treatment period + 1 and stops on either (1) the completion date of follow-up period in eCRF; (2) the last known study date if the subject is lost to follow-up.

For efficacy analysis, only the open-label treatment period will be used.

For safety analysis, the open-label treatment period and observational follow-up period will be included into the data summary.

5.4. Baseline Definitions

For all MRI assessments (MRI of the most affected hand, WB-MRI, and [REDACTED]), the baseline is defined as nominal baseline result from IAG. For other assessments related to efficacy endpoints and baseline disease characteristics, the baseline is defined as the last value measured on or before the day of the first dose of IP.

For safety analyses, the baseline is defined as the last value measured on or before the day of the first dose of IP.

5.5. Time Points

Time points in all analyses are based on the visits/study weeks as recorded in the database. Appropriate dates (e.g., date of measurement or date of specimen collection) will first be used to ensure only data (including data from scheduled, unscheduled and discontinuation) measured or collected within the specific analysis period (Section 5.3) are included, and then the visits/study weeks as recorded in the database will be used to assign one value (possibly missing) to each time point at the subject level according to the following rules:

Scheduled Visits

- If the value at a scheduled visit is missing but a value is available at an associated unscheduled visit, the value from the associated unscheduled visit will be used for the

study week. If values from more than one associated unscheduled visit (e.g., Visits 8.01 and 8.02) are available, then the one from the first associated unscheduled visit (e.g., Visit 8.01) will be used for the study week.

- If the value at a scheduled visit is missing and there is no value available from an associated unscheduled visit, the value at the study week will be missing.
- Please note that unscheduled visits are recorded to one general visit code. The visit numbering for unscheduled visits will be re-numbered based on the unscheduled visit date (and time) comparison to the schedule visit date (and time). If the unscheduled record falls in between two scheduled visits, the re-numbered value will be assigned. For example, if the unscheduled visit date is “on or after visit 1” AND “prior to visit 2”, then the re-numbered value will be 1.01. If there are multiple unscheduled visits in that interval, the unscheduled visit date (and time) will be used to ordered the re-number values like 1.01, 1.02, 1.03, so on.

Early Termination Visit

- A value from the early termination visit will be mapped to the next scheduled visit after the last visit the subject has completed.

Unscheduled Visit

- Please note that only vital signs, local lab data, central lab data and procedures MRI will have unscheduled visits and each unscheduled visit will be recorded to one specific visit code.

Analysis Visit Window for Safety Data

For safety analyses, all available values obtained between 2 planned visits including unscheduled measurements will be pooled to the analysis visit window according to the following definition:

Table 2: Analysis visit window for Safety Data

Visit Number	Visit Name	Target Day	Analysis Window for Safety Data
1	Screening (1)	<1	<1
2	Baseline (2)	1	1
3	Week 8 (3)	56	[2, 84]
4	Week 16 (4)	112	[85, 140]
5	Week 24 (5)	168	[141, 210]
6	Week 36 (6)	252	[211, 294]
7	Week 48 (7)	336	[295, 350]

For multiple measurements in the same visit category, the value measured nearest to the target day will be assigned to the visit; if they are at the same distance to the target day, the latest one will be used.

[figure not shown]
For the efficacy data, no analysis window will be mapped, and the nominal visit will be used.

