g For dactylitis assessment at screening, only a binary evaluation is needed (yes/no). As per inclusion criteria, subjects must have  $\geq 3$  swollen AND  $\geq 3$  tender joints, with hand involvement (defined as  $\geq 1$  swollen joint OR dactylitis). For the subsequent visits, LDI is needed.

h BASDAI will be performed for all subjects.

i The clinical and the MRI assessments should be performed on the same day, with the MRI scans always performed after the clinical visit. Exceptionally, MRI scans can be performed within 7 days after the clinical assessments. The baseline MRI must be performed within 7 days after the first administration of IP. The subsequent MRIs should be performed at Week 24 + 7 days and Week 48 + 7 days.

j As per protocol, in case of early termination, the site must perform all due assessments, including the MRI scans, to the best of its ability. Early termination MRI assessments will not be performed if the previous MRI scans have been done within the last 8 weeks before the early termination visit.

Approved

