4.2.1.1. Primary Efficacy Endpoint

The primary endpoint of the study is the change from baseline in the composite score of bone marrow edema (BME), synovitis, and tenosynovitis assessed by Psoriatic Arthritis Magnetic Resonance Imaging Score (PsAMRIS) at Week 24.

[figure not shown]

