4.2.4.2. MRI of the Most Affected Hand

The conventional MRI assessment will be performed at baseline, Week 24, Week 48 and ET visit on the hand with the greater inflammatory burden of swollen joints and/or dactylitis. If both hands are equally affected, the dominant hand will be designated as the index hand.

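### The SAP maps early-termination values to the next visit of any kind, so read literally some ET MRIs land on Week 16 or 36, where no MRI is scheduled, and miss the Week 24 or Week 48 endpoint

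*SAP*

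**What the plan says.** The mapping rule for subjects who stop early is in SAP 5.5: "A value from the early termination visit will be mapped to the next scheduled visit after the last visit the subject has completed." It makes no exception for assessments done at only some visits. The same section adds: "For the efficacy data, no analysis window will be mapped, and the nominal visit will be used."

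On-treatment visits fall at Weeks 8, 16, 24, 36 and 48 (Protocol Table 13; SAP 5.5, Table 2). MRI follows a sparser schedule. For the hand, SAP 4.2.4.2 says: "The conventional MRI assessment will be performed at baseline, Week 24, Week 48 and ET visit." Table 13 gives whole-body MRI the same schedule, and its footnote i says: "The subsequent MRIs should be performed at Week 24 + 7 days and Week 48 + 7 days." Footnote j asks sites to scan at early termination as far as they can, but such a scan "will not be performed if the previous MRI scans have been done within the last 8 weeks before the early termination visit."

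The primary endpoint is the change in the composite score "assessed by Psoriatic Arthritis Magnetic Resonance Imaging Score (PsAMRIS) at Week 24". All other visible MRI endpoints are at Week 24 or Week 48. SAP 4.2.4.4.2 treats a PsAMRIS total with no result in the visit window as missing and does not impute it.

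Table 13 schedules BASDAI and PsAID-12 at baseline, Weeks 8, 24 and 48, and ET, but not at Weeks 16 or 36.

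**The concern.** The ET scan exists so that a subject who stops can still contribute imaging data. A rule that counts visits of every kind sends some of these scans to a visit with no MRI endpoint, and no visible rule brings them back.

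What is at stake is who enters the Week 24 summary. Subjects who stop for adverse events or lack of efficacy shortly after Week 16 are kept, and those who stop shortly before it are not. The dividing line is a clinic visit with no imaging purpose. A missed visit can have the same effect: a subject who completed Week 8, missed Week 16 and stops at Week 22 has a nearly on-time scan assigned to Week 16.

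The mITT set does not reveal the loss. It requires only that subjects "have baseline and at least one postbaseline of primary efficacy endpoint PsAMRIS", with no visit named. A subject stopping in Weeks 8-16 can therefore qualify and still supply no Week 24 value.

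**Working it through.** **1. The plan's own figure.** Inputs from SAP 4.3 and Protocol 9.3: N = 120, dropout 20%, SD 6.2, two-sided 95% interval. Evaluable n = 120 × 0.80 = 96. Half-width = 1.96 × 6.2 / √96 = 1.240, which agrees with the stated 1.24. The sample size thus already allows for all 24 dropouts contributing nothing.

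**2. The ET rule applied literally to MRI** (nominal schedule, no missed visits, 8-week exclusion from footnote j):

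| Stop | Last completed visit | Last scan | ET scan due | Mapped to | Used at a visible endpoint |
|---|---|---|---|---|---|
| Weeks 0-8 | Baseline | Baseline | No | - | - |
| Weeks 8-16 | Week 8 | Baseline | Yes | Week 16 | No |
| Weeks 16-24 | Week 16 | Baseline | Yes | Week 24 | Yes |
| Weeks 24-32 | Week 24 | Week 24 | No | - | - |
| Weeks 32-36 | Week 24 | Week 24 | Yes | Week 36 | No (own Week 24 scan kept) |
| Weeks 36-48 | Week 36 | Week 24 | Yes | Week 48 | Yes |

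The limits are nominal. Visit windows of ±1 week and scans up to 7 days after the visit move them by 1-2 weeks.

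**3. Number affected.** The documents do not say when dropout occurs, so two even spreads of the 24 dropouts are assumed, with every due ET scan obtained.

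- *Case A, all 24 stop within Weeks 0-24 (1 per week).* Weeks 8-16: 8 subjects. Weeks 16-24: 8 subjects. Week 24 n is 96 + 8 = 104 under the literal rule, half-width 1.96 × 6.2 / √104 = 1.19. Mapping to the next MRI visit gives 112, half-width 1.15.
- *Case B, 24 stop over Weeks 0-48 (0.5 per week).* Weeks 8-16: 4. Weeks 16-24: 4. Weeks 32-36: 2. Weeks 36-48: 6. ET scans made: 4 + 4 + 2 + 6 = 16, of which 4 + 2 = 6 (38%) reach no visible endpoint. Week 24 n: 108 + 4 = 112 (1.15) under the literal rule, 116 (1.13) when remapped. Week 48 n: 96 + 6 = 102 (1.20), then 104 (1.19).

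**4. BASDAI and PsAID-12.** The 8-week exclusion applies only to MRI. An ET value goes to Week 16 if the last completed visit is Week 8, and to Week 36 if it is Week 24, which covers stops anywhere in Weeks 24-36. In Case B that is 0.5 × 8 = 4 values lost to Week 24 and 0.5 × 12 = 6 lost to Week 48. For BASDAI these are upper figures, because the endpoint is limited to a subgroup.

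**The case against.** **The analysis text that matters most is not visible.** SAP 4.2.4.4.2 refers missing data to 6.1. There the sensitivity analyses rely on an analysis model that does not appear in the text, and 6.2.2.1 describes the primary analysis as involving scanner type, baseline score and time. If time is continuous in that model, a Week 16 or 36 value could still inform the Week 24 or 48 estimate. This stands. A reader might infer that the affected scans contribute nothing to the primary result. The documents support that only for summaries by visit, or for a model with visit categories at Weeks 24 and 48.

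**A programmer might read 'next scheduled visit' as the next visit for that assessment.** That would be sensible, but SAP 5.5 does not say it, and the intention should be written down.

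**The numbers are small and assumed.** This stands. Even in Case A, the literal rule gives a half-width of 1.19, better than the planned 1.24, and remapping gains only 0.04. A reader might also infer a material bias. If the 8 recovered subjects in Case A changed 3 to 6 points less favourably than the rest, the mean would move by 8/112 × 3 = 0.21 to 8/112 × 6 = 0.43. Nothing in the documents supports a gap of that size, so this is not a finding.

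**An early scan may be a poor stand-in for Week 24.** A Week 9 scan mapped to Week 24 is 15 weeks early. Whether that is acceptable is a choice about what is being estimated, and the point here does not settle it. The SAP already accepts such mapping for a Week 17 scan, so the remedy extends its own convention and needs a repeat analysis without the mapped scans.

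**Conclusion.** The point holds on the wording of SAP 5.5. Read literally, ET hand and whole-body MRIs go to Week 16 when the last completed visit is Week 8 (stopping at about Weeks 8-16), and to Week 36 for stops at about Weeks 32-36. The first group misses the primary Week 24 endpoint. A reader might infer that the second group loses both time points, but those subjects normally have their own Week 24 scan and lose Week 48 only. BASDAI and PsAID-12 have the same fault at Weeks 16 and 36.

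About 4 to 8 subjects are affected at Week 24 and about 2 at Week 48. This rests on evenly spread dropout, no missed visits and complete ET scanning, none of which the documents give. The sample size is not in question. The fault is that inclusion in the primary summary depends on visit numbering, and it should be corrected before database lock. How far it affects a model-based estimate remains open.

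**What to change.** Replace the ET sentence in SAP 5.5 with a rule to this effect: *an early-termination value is assigned to the first visit, following the subject's last completed visit, at which Protocol Table 13 schedules that assessment, provided that visit holds no value already.*

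Keep the last completed visit as the starting point and do not reassign by date alone. For a subject who completed Week 16, missed Week 24 and is scanned at Week 26, a date rule would send the scan to Week 48, 22 weeks away. The rule above keeps it at Week 24, 2 weeks away.

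Also:
- State that the visit-window wording in SAP 4.2.4.4.2 does not exclude mapped ET scans. Read strictly, it could remove even those from Weeks 16-24.
- Report the number and study day of mapped ET scans at Weeks 24 and 48.
- Repeat the primary summary without the mapped scans.

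The cost is one sentence of SAP text, one programming rule and one repeated table, with no new data. The downside is that some Week 24 values will come from scans made as early as Weeks 8-16, and after a missed Week 24 visit a few may be late (a Week 34 scan would still be labelled Week 24). The study-day report and the repeat analysis show both.
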